We hope to determine how regular cannabis use alters resting brain activity in people with MS.

c) **Proposed Start Date (may not precede IRB approval date):**

August 2016

2.

Study Procedures (If this is a student project, the methods section of the thesis or dissertation proposal must be attached in section #16 - Attachment section.)

a) **In lay language, describe all the procedures, from screening through end-of-study, that the human subject must undergo in the research project, including study visits, drug treatments, randomization and the procedures that are part of standard of care. Please note: Do NOT respond "See Attachment Section." If you would like to add tables, charts, etc., attach those files in the Attachment section (#16).**

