**\*\*\* Subject Population (a-g) \*\*\***

8.

Subject Population - In the space below, please detail the participants that you are requesting to recruit (include requested participant number and description of each group requested). (Input N/A if not applicable)

- a) **Requested Participant Description (Include number of participants that you plan to study and description of each group requested, if applicable).**

We plan on recruiting 40 people with MS: 20 are regular cannabis users (smokers), 20 are not users, with an estimate that approximately 5 from each group will not complete the study (i.e. drop out).

- b) **What is the rationale for studying the requested group(s) of participants?**

To investigate the effects of medical marijuana usage on physical function we will employ an observational case-control design. Cases (MS medical marijuana users) will be compared to age, sex, and disease duration matched controls (MS non-cannabis users). The research team has experience with all the methods involved.

- c) **If applicable, state the rationale for involvement of potentially vulnerable subjects to be entered into the study, including minors, pregnant women, economically and educationally disadvantaged, or decisionally impaired subjects. Specify the measures being taken to minimize the risks and the chance of harm to the potentially vulnerable subjects.**

N/A

- d) **If women, minorities, or minors are not included, a clear compelling rationale must be provided. Examples for not including minors: disease does not occur in children; drug or device would interfere with normal growth and development; etc.**

N/A

- e) **State if any of the subjects are students, employees, or laboratory personnel. They should be presented with the same written informed consent. If compensation is allowed, they should also receive it.**

N/A

- f) **Describe how potential subjects will be identified for recruitment (e.g., chart review, referral from individual's treating physician, those individuals answering an ad). How will potential participants learn about the research and how will they be recruited (e.g., flyer, email, web posting, telephone, etc.)? Attach recruitment materials in the Attachment Section (#16). Important to remember: potential subjects may not be contacted before IRB approval.**

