### *Statistical Analysis*

All data are reported as Mean (Standard Deviation) unless otherwise noted. Pearson's correlations were calculated between demographic variables (age, height, weight, BMI, disease duration) and whole brain SUV to identify possible covariates for the SPM analysis. Significant factors were individually tested as covariates during SPM analysis.

Demographic, clinical, and extracted regional SUV variables were compared between the two groups using unpaired student's t-tests. If a clinical variable differed between the two groups a Pearson's correlation was performed with it and regional SUVs. Cohen's D measures of effect size were calculated for the regional SUVs. Analysis was performed using IBM SPSS Statistics for Windows version 24 (IBM Corp., NY, USA) with alpha set to 0.05.

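### The regional SUV t-tests and Cohen's d carry no covariate, although a demographic factor that passes the plan's own screen is tested as a covariate in SPM

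*Combined protocol and SAP*

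**What the plan says.** All the analysis text is in the Statistical Analysis section at the end of the combined document. It has two routes for SUV.

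- **SPM route.** "Pearson's correlations were calculated between demographic variables (age, height, weight, BMI, disease duration) and whole brain SUV" in order to find candidate covariates. Then: "Significant factors were individually tested as covariates during SPM analysis".
- **Regional route.** "Demographic, clinical, and extracted regional SUV variables were compared between the two groups using unpaired student's t-tests", and "Cohen's D measures of effect size were calculated for the regional SUVs". No covariate is named for either.

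The one follow-up in the regional paragraph is: "If a clinical variable differed between the two groups a Pearson's correlation was performed with it and regional SUVs". It applies to clinical variables. Nothing is said about what happens if a demographic variable differs. Alpha is 0.05.

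On design, Subject Population item 8(b) describes an observational case-control study: "Cases (MS medical marijuana users) will be compared to age, sex, and disease duration matched controls (MS non-cannabis users"). Item 1(b) of the Purpose section gives the imaging aim: "We hope to determine how regular cannabis use alters resting brain activity in people with MS". The session procedures in item 2(a) describe no imaging, so it is an assumption that this matching applies to the participants who were imaged.

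**The concern.** The plan treats the same set of factors in two ways. If a factor correlates with whole brain SUV, the plan considers it important enough to try in SPM. The regional comparison of the same images then proceeds as if that factor did not exist.

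Users and non-users chose their exposure. Three of the five screened factors (height, weight, BMI) are not matched, so nothing in the design holds them equal. The Pearson correlation that follows a clinical difference describes an association. It does not adjust the group contrast, and it is not stated for demographic variables.

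Two things are at stake. A regional difference and its Cohen's d could be read as a cannabis effect when part of it comes from a demographic factor. And a disagreement between the SPM map and the regional table could arise only because one is adjusted and the other is not.

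**Working it through.** The documents give no power, effect size or expected SUV difference, so there is no figure of the plan's to reproduce. What follows is an illustration.

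**Inputs from the documents**
- Alpha 0.05; two-sided is assumed, as the section does not say.
- Group size: item 8(a) plans 20 per group and expects that "approximately 5 from each group will not complete the study (i.e. drop out"), which leaves 20 - 5 = 15. The continuing review form submitted in June 2017 reports 6 participants studied, all users. The number imaged is not stated, so 6, 15 and 20 per group are all shown.

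**Assumed inputs**
- One covariate, within-group SUV SD of 1, and no true cannabis effect.
- Covariate effect *b* of 0.3 to 0.4 SD of SUV per SD of the covariate.
- Group imbalance *m* of 0.5 to 0.8 SD in the covariate.

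**Step 1: spurious regional difference** = *b* × *m*. This gives 0.3 × 0.5 = 0.15, 0.4 × 0.5 = 0.20, 0.3 × 0.8 = 0.24 and 0.4 × 0.8 = 0.32 SD.

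**Step 2: type I error of the unpaired t-test.** Noncentral t with 2n - 2 degrees of freedom and noncentrality *d* × √(n/2). For example, at n = 15 and *d* = 0.32 the noncentrality is 0.32 × √7.5 = 0.876, with 28 degrees of freedom and critical t 2.048.

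| Spurious difference (SD) | 6 per group | 15 per group | 20 per group |
|---|---|---|---|
| 0 | 5.0% | 5.0% | 5.0% |
| 0.15 | 5.6% | 6.8% | 7.5% |
| 0.20 | 6.1% | 8.3% | 9.5% |
| 0.24 | 6.7% | 9.7% | 11.5% |
| 0.32 | 7.9% | 13.5% | 16.7% |

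A stronger assumed link gives more: 0.7 × 0.8 = 0.56 SD would give 32% at 15 per group and 41% at 20. The documents support that no better than they support zero.

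**Step 3: with the covariate in the model.** Simulating SUV on group plus the covariate gives an error of about 5% and a mean adjusted difference of about 0 at 6, 15 and 20 per group.

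**Step 4: would the demographic t-tests reveal the problem?** Power to detect an imbalance of 0.5 to 0.8 SD is 12-24% at 6 per group, 26-56% at 15 and 34-69% at 20. A non-significant line in the demographic table is therefore weak reassurance, and the plan states no action even if it is significant.

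**Step 5: what the plan's screen can catch.** The threshold is |r| = t / √(N - 2 + t²). It is 0.576 at total N = 12, 0.361 at N = 30 and 0.312 at N = 40. Under the assumptions above, with an assumed residual correlation of 0.8 between whole brain and regional SUV, simulation has the screen flag the factor in 39-67% of studies at 15 per group and 51-80% at 20.

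**The case against.** Several points on the other side have force.

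- **A reader might infer that SPM retains the covariate.** The text says only that significant factors were tested one at a time. It does not say that any passed the screen or stayed in a final model. This stands, and the point is worded accordingly. It does not help the regional t-test, which has no covariate whatever SPM kept.
- **A reader might infer that demographic factors are never adjusted for.** That is wrong: they have a route into SPM. The gap is in the regional comparison.
- **A reader might infer that body size did confound the result.** The documents show neither an imbalance nor an effect of body size on SUV. They do not say how SUV was normalised, so weight may already be partly accounted for. Matching on sex plausibly limits height and weight differences. The screen uses whole brain SUV, so a link to a given region is itself inferred. All of this stands.
- **The regional tests may only describe the SPM result.** The section does not say. If regions were picked from SPM, the error rates above, which are for one pre-specified region, do not describe the test. Cohen's d would still carry any imbalance.
- **The sample may be small.** With 6 studied by mid-2017 and the record closed on 05/30/2018, the imaged groups may be well below 15. The inflation is then smaller (about 6-8% at 6 per group), while a covariate costs relatively more.

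**Conclusion.** The point holds in conditional form. The regional t-tests and Cohen's d have no covariate, a factor that passes the plan's screen is tried only in SPM, and no other section adds an adjustment. If such a factor differs between the groups, the regional difference may partly reflect it.

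The size is modest under the assumptions used: a spurious difference of 0.15 to 0.32 SD, and a type I error between about 6% and 17% depending on group size. It is nil if the groups are balanced on the factor. These figures rest on assumed values for the covariate effect, the imbalance and the number imaged. The unmatched status of height, weight and BMI matters only if the stated matching applies to those imaged.

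It may be tempting to conclude that weight must be adjusted for whatever the screen shows. The documents do not support that. They give no evidence of a weight effect and leave the normalisation open, and forcing weight in would override the plan's selection rule and could place weight beside a flagged BMI.

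**What to change.** For each extracted region, add a linear model of regional SUV on group plus any demographic factor that passes the plan's own screen. Use the same covariates as in SPM, and say which they were. Enter only one of height, weight and BMI, and do not force in weight if it does not pass. Report the adjusted difference with its 95% CI and an adjusted standardised difference beside the unadjusted t-test and Cohen's d, and give the number imaged per group. State whether the regional tests carry inference or describe the SPM result.

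The section is in the past tense and the record is closed. If the data have already been analysed, label this a sensitivity re-analysis.

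**Cost.** No new data are needed, since every candidate is on the plan's list. Each covariate takes one residual degree of freedom: at 15 per group, 28 to 27, with critical t moving from 2.048 to 2.052. For a covariate unrelated to SUV and an assumed true difference of 0.8 SD at 15 per group, power falls from 56% to about 55% with no imbalance. With a 0.8 SD imbalance the standard error grows by about √(1 + 0.8²/4) = 1.08 and power falls to about 49% (48% by simulation). That loss is a reason to keep the covariate set small.

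**Limit.** A factor that the screen misses stays out of the model, so this reduces the problem without removing it.

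### The SAP does not say how the regions for the regional SUV t-tests and Cohen's d were chosen: if from the SPM group result, the tests are circular; if several were fixed in advance, multiplicity is uncontrolled

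*Combined protocol and SAP*

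**What the plan says.** The imaging analysis is described only in the short Statistical Analysis section at the end of the combined document. Candidate covariates for the SPM analysis are demographic variables that correlate with whole-brain SUV, and "Significant factors were individually tested as covariates during SPM analysis". The section then says that "extracted regional SUV variables were compared between the two groups using unpaired student's t-tests" and that "Cohen's D measures of effect size were calculated for the regional SUVs". The software statement closes "with alpha set to 0.05". The regional values are used once more: "If a clinical variable differed between the two groups a Pearson's correlation was performed with it and regional SUVs".

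The section names no atlas or region list, no SPM contrast, threshold or correction, and no adjustment for the number of regions. It does not say that the regional tests are descriptive. The unpaired t-tests carry no covariate.

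Elsewhere, section 1(b) of the protocol (Purpose, Study Procedures, Background) gives the imaging aim: "We hope to determine how regular cannabis use alters resting brain activity in people with MS". Section 8(a) (Subject Population) gives the only group sizes: "20 are regular cannabis users (smokers), 20 are not users, with an estimate that approximately 5 from each group will not complete the study".

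**The concern.** An SPM analysis searches many voxels. If regional SUVs are then taken from the places where users and non-users differed most, a t-test of users against non-users in the same people repeats the criterion by which the region was chosen. Its p-value no longer has its nominal meaning, and d cannot fall below a floor set by the SPM threshold and the sample size.

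The imaging aim makes users versus non-users the natural SPM contrast, so this route is open under the plan as written. A reader of the results could not tell an unbiased d from one with a built-in floor above 1. Such a d could then be used to size a later study, which would be too small.

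The regional values also enter the correlations with any clinical variable that differs between groups. If both variables were picked because the groups differ, a pooled correlation can arise from that shared difference alone.

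**Working it through.** The plan gives no power, effect size or SPM threshold for the SUV analysis, so there is no figure to reproduce. The size of the problem is worked out under each reading of how the regions were chosen.

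**Inputs**
- From the documents: alpha 0.05; unpaired Student's t-test; 20 per group with about 5 lost, so 20 − 5 = 15.
- Assumed: 15 or 20 scanned per group. Section 8(a) gives these numbers for the whole study; the number scanned is not stated.
- Assumed: two-sided voxel threshold p<0.001. No threshold is stated.
- Assumed: true d = 0.5, for illustration.

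**Reading A: regions taken from the SPM group contrast**

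*Floor on d.* With n per group, d = t × √(2/n). A voxel passing the threshold therefore has |d| ≥ t_crit × √(2/n), with 2n − 2 degrees of freedom.
- n = 15: t_crit (28 df) = 3.674; √(2/15) = 0.3651; floor = **1.34**.
- n = 20: t_crit (38 df) = 3.566; √(2/20) = 0.3162; floor = **1.13**.

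The floor carries over to the mean of a cluster whose voxels all pass in the same direction. The group difference in the cluster mean is the average of the voxel differences, and the SD of the cluster mean cannot exceed the average of the voxel SDs. The floor is exact for an SPM contrast without covariates; with covariates it applies to the adjusted effect.

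*Mean d after selection.* With true d = 0.5, t follows a noncentral t distribution with noncentrality 0.5 × √(n/2). Averaging d over draws with two-sided p<0.001 gives:
- n = 15: mean reported d = **1.52**, and 1.52/0.5 = 3.0 times the true value.
- n = 20: mean reported d = **1.28**, and 1.28/0.5 = 2.6 times the true value.

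*Simulation under no true difference.* Smooth 32×32×32 fields (FWHM 3 voxels), 150 runs per setting. The largest cluster at p<0.001 uncorrected was extracted and re-tested on the same data.

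| n per group | Re-test p<0.05 | Mean \|d\| | Same mask, new data: p<0.05 | Same mask, new data: mean d |
|---|---|---|---|---|
| 15 | 100% | 1.89 | 4.0% | 0.00 |
| 20 | 100% | 1.55 | 6.7% | −0.01 |

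The bias comes from using the same data twice. It disappears when the regions are independent of the data tested.

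**Reading B: several regions fixed in advance**

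Each d is then free of selection bias and each test has its nominal 5% error. A single fixed region gave p<0.05 in 5.3% (n = 15) and 3.3% (n = 20) of the null runs. Over m independent regions, familywise error is 1 − 0.95^m:
- m = 5: 22.6%
- m = 10: **40.1%**
- m = 20: **64.2%**

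The number of regions is not stated, and positive correlation between regions would generally lower these figures.

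**The case against.** The strongest reply is that circularity is not shown. Extracting values fits an atlas as well as SPM clusters, and the section states neither the SPM contrast nor the source of the regions. That stands. A reader might infer that the study did re-test its own SPM clusters; the documents do not support that. They show only that nothing rules it out.

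A second reply is that the SPM step may have been familywise-corrected. False detection would then be controlled at that step, but the second p-value and d would still be conditional on selection. A stricter threshold raises the floor: Bonferroni over an assumed 500 resolution elements gives 1.65 at 15 per group and 1.37 at 20.

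A third is that the magnitudes rest on assumed values. That also stands. The three visits described in the protocol contain no imaging and the radioisotope item is answered NO, so 15 and 20 per group are borrowed from the motor-function study.

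Two other inferences go too far. One could take the largest of 20, 50 or 200 null regions and read the resulting 64%, 92% and nearly 100% significance rates as the effect of circularity. They are ordinary multiplicity, 1 − 0.95^m, and a fixed atlas tested without adjustment would share them. Nor is d the only effect size in the section, since Pearson correlations with the regional SUVs are also calculated.

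On covariates, the text says that factors were tested individually, not that any was kept. The unadjusted t-test is inconsistent with the SPM model only if one was retained.

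**Conclusion.** The point holds as a gap with two branches. If the regions come from the SPM group contrast, the t-test p-values are too small and d too large, with a floor on |d| of 1.34 or 1.13 and a mean reported d of 1.52 or 1.28 when the true value is 0.5. These figures depend on the assumed p<0.001 threshold and 15 or 20 scanned per group. If several regions were fixed in advance, there is no circularity, but familywise error is about 40% for 10 and 64% for 20 independent regions. Only a single region fixed in advance would escape both problems, and the section speaks of regional variables in the plural. The regional p-values therefore cannot be taken at face value on either branch. Whether d is biased depends on a choice that the plan does not disclose. This should be corrected; it does not show that the reported results are wrong.

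**What to change.** State how the regions were defined, and then:

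- Base the regional t-tests and d on an atlas or region list chosen without reference to the SPM group contrast. Name it and give the number of regions.
- Include in those comparisons any covariate retained in the SPM model, so that both analyses address the same adjusted difference.
- Adjust for the number of regions, by Holm if familywise error is to be controlled or by a false discovery rate procedure if the aim is exploratory.
- For clusters derived from the SPM result, rely on the corrected SPM inference. Show extracted values and any d as descriptive, labelled as selected, without a second p-value.

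The section is written in the past tense and the Event History shows the protocol closed on 05/30/2018, so this may have to be done as disclosure and re-analysis. A complete published atlas remains usable then, because its regions do not depend on the contrast. The cost is a few sentences and one extraction from the existing images, with no new data. The downside is that reported effects will probably be smaller and fewer regions significant.

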Prospective participants will be recruited from the Integrative Neurophysiology Laboratory's (INPL) participant database, the clinical practice of [name], Banner Health, Greeley CO, and through advertisements in the Colorado and Wyoming Chapter of the National MS Society newsletters. All experimental procedures will be performed in the INPL (Director: [name], FACSM). Interested individuals will perform an initial screening via an online questionnaire, hosted by Qualtrics, which has a contract with the College of Health and Human Sciences. Contact information for the prospective participants' information will be accessible only to the research staff according to HIPPA regulations. After completion of the online screening form, INPL personal will contact eligible participants via phone and establish 20 case/control matched pairs, 40 total participants. After the pair has been identified INPL staff will schedule the participants' first visit. Eligibility requirements for this study are: medically diagnosed with MS, 30-75 years of age, Moderate disability (Patient Determined Disease Steps score 2-6). Cases will verbally confirm their usage of medical marijuana before matching is conducted. We will only recruit people with MS who smoke medical marijuana. Exclusion criteria include: relapse with the last 60 days; high risk for cardiovascular disease (American College of Sports Medicine risk classification); changes in disease modifying medications within the last 45 days; concurrent neurological/neuromuscular disease, concurrent conditions unrelated to MS that would exacerbate fatigue (anemia, hypothyroidism, shiftwork-related fatigue, B12 deficiency, major sleep disorder, or major depressive disorder); history of traumatic brain injury, seizure disorders, hydrocephalus, traumatic brain injury; diabetes; hospitalization within the last 90 days; alcohol dependence (>2 drinks per day); present history (last six months) of drug abuse; and inability to understand/sign informed consent. Additional participants may be screened and recruited if problems arise within a matched pair, e.g. participants drop out or are unable to meet time commitments.

Medical Marijuana users will be asked to refrain from using cannabis for 8 hours prior to all testing and training to prevent any behavioral/physiological effects of acute intoxication which result from THC.

The experimental protocol for this study consists of three testing sessions.

Session 1

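### The planned two-group comparisons use the pooled-variance Student's t-test; if the groups finish unequal in size and in spread, its level drifts modestly from 5%, and Welch's test removes that risk at almost no cost

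*Combined protocol and SAP*

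**What the plan says.** The Statistical Analysis section names one method for comparing users with non-users. Demographic measures, clinical measures and regional SUVs were "compared between the two groups using unpaired student's t-tests", "with alpha set to 0.05". It mentions no Welch version and no rule for unequal variances. Sidedness is not stated; two-sided is assumed here.

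On group sizes, Study Procedures (section 2a) says that staff will "establish 20 case/control matched pairs, 40 total participants". Section 8(a) adds dropout, "with an estimate that approximately 5 from each group will not complete the study". Section 2(a) also allows for replacement: "Additional participants may be screened and recruited if problems arise within a matched pair". Item 1 of the continuing review form records 6 people studied, all users, with 14 users and 20 non-users still to be studied.

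The documents do not state the final analysed group sizes, the number per group who contributed SUV data, or the SD of any outcome in either group.

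**The concern.** Student's unpaired test estimates one common variance and uses it for both groups. If sizes and variances both differ, the standard error is wrong. It is too small when the smaller group is the more variable one, which gives too many false positives. It is too large in the opposite case, which costs power.

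Neither condition that protects the test is secured. Dropout is an estimate and need not fall equally on the two groups. Replacement is permitted but not required. Nothing in the plan says that the spread should be the same in users and non-users.

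The test also acts as a filter. A clinical variable found to differ between the groups goes on to be correlated with regional SUVs, so a drifting level would also affect which follow-up analyses are run.

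**Working it through.** **Inputs from the documents.** Alpha 0.05 (Statistical Analysis). Planned sizes 20 and 20 (section 2a). Dropout about 5 per group (section 8a), so 20 − 5 = 15 per group, or 15 vs 20 if only one group loses 5.

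**Input assumed.** The ratio of the group SDs, because no SD is given: 1, 1.5 and 2. Data are taken as normal, groups as independent, with no true difference in means.

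**Step 1: the stated level.** With equal SDs the pooled test has a level of exactly 5% whatever the sizes. The calculation returns 5.0% for 20 vs 20, 15 vs 15 and 15 vs 20, so the stated alpha is reproduced.

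**Step 2: why size matters.** The pooled test estimates the variance of the mean difference as s²p × (1/n1 + 1/n2), where s²p = [(n1−1)s1² + (n2−1)s2²] / (n1+n2−2). The true variance is σ1²/n1 + σ2²/n2.

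- Equal sizes n: the expected estimate is (σ1²+σ2²)/2 × 2/n = (σ1²+σ2²)/n, which equals the true value. Only the degrees of freedom are slightly too generous.
- 15 vs 20, SD ratio 2, smaller group more variable (variances 4 and 1): s²p = (14×4 + 19×1)/33 = 2.273. The estimate is 2.273 × (1/15 + 1/20) = 0.265. The true value is 4/15 + 1/20 = 0.317. The estimated variance is 0.84 of the true one, so the test is too liberal.
- 15 vs 20, SD ratio 2, larger group more variable (variances 1 and 4): s²p = (14×1 + 19×4)/33 = 2.727. The estimate is 2.727 × (1/15 + 1/20) = 0.318. The true value is 1/15 + 4/20 = 0.267. The estimated variance is 1.19 times the true one, so the test is too strict.

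**Step 3: the actual level.** The level is the average of 2Φ(−t* × SEpooled / SEtrue) over the sampling distributions of s1² and s2² (scaled chi-square), where t* is the 97.5% point of t on n1+n2−2 degrees of freedom. Welch's test was evaluated in the same way with its own standard error and degrees of freedom.

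| Sizes | SD ratio | Student, smaller group more variable | Student, larger group more variable | Welch |
|---|---|---|---|---|
| 20 vs 20 | 1.5 | 5.1% | 5.1% | 5.0% |
| 20 vs 20 | 2 | 5.2% | 5.2% | 5.0% |
| 15 vs 15 | 1.5 | 5.1% | 5.1% | 5.0% |
| 15 vs 15 | 2 | 5.3% | 5.3% | 5.0% |
| 15 vs 20 | 1.5 | 6.5% | 4.0% | 5.0% |
| 15 vs 20 | 2 | 7.5% | 3.5% | 5.0% |
| 10 vs 20 | 2 | 11.4% | 1.9% | 4.9% to 5.1% |

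In the equal-size rows the two Student columns are the same by symmetry.

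**Step 4: price of switching.** With 15 per group, equal SDs and a true difference of 0.8 SD (an illustrative value), power is about 56% for either test. Welch is lower by about 0.2 points.

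**The case against.** The plan is balanced by design. It sets matched pairs, expects similar dropout in both groups, and allows replacement when a pair breaks, which works toward equal sizes. In that setting Student's test is within 0.3 points of 5% even with a two-fold SD ratio. This stands, and it is why the point is minor.

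A reader might infer a much larger problem, with error rates from about 2% to 11%. The documents do not support that. The range needs 10 vs 20 together with a two-fold SD ratio, and nothing in the documents predicts either. The 6-to-0 count in the continuing review is a mid-recruitment figure. The same item leaves 14 users and 20 non-users to come, which restores 20 vs 20.

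The case for unequal spread is also only a possibility. Both groups have the same disability eligibility range, which by itself suggests no difference in spread. Varying cannabis exposure among users adds outcome variance only if cannabis affects the outcome.

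A last objection is that Welch's test does not by itself deliver 5% here, because the groups are matched on age, sex and disease duration. With 15 to 20 pairs, equal SDs and an assumed within-pair correlation of 0.2 to 0.4, an unpaired test has a true level of about 3.0% down to 1.4%, and Welch's is about the same. This stands too. The pairing needs its own remedy, and the recommendation here is limited to comparisons left unpaired.

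**Conclusion.** The point holds as a minor improvement. The section names only the pooled-variance test, and the documents neither guarantee equal analysed groups nor state how many people per group were scanned.

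If the groups finish equal, little is at stake. If one group alone loses 5, the level departs from 5% by about 1 to 1.5 points at an SD ratio of 1.5 and by 1.5 to 2.5 points at a ratio of 2, in a direction that cannot be known beforehand. These figures rest on the assumed SD ratios, normal data, two-sided testing and independent groups.

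The point covers the three kinds of variable that the section lists for t-tests. It does not reach the voxel-wise SPM analysis, whose test is not specified.

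**What to change.** In the Statistical Analysis section, state that every two-group comparison left unpaired uses Welch's unequal-variance t-test by default, and that the choice does not depend on a preliminary test of variances. Any comparison analysed as matched pairs should use a paired method instead. Report the number analysed in each group for every outcome, including the number with SUV data.

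The cost is one phrase of text and about 0.2 points of power when variances are equal. SPSS, the named software, prints the unequal-variance result beside the Student result. Fixing the choice also stops it being made between the two printed rows once results are seen. The section is written in the past tense and the event history shows the protocol closed, so if the analysis is already done, the Welch result can be reported from the same output with a note that it replaces the Student result throughout. Any clinical variable whose significance changes would then need its follow-up SUV correlation reconsidered.

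### Clinical variables chosen because they differ between users and non-users are correlated with regional SUVs with no stated adjustment for group, so a pooled r mixes group differences with any within-group link

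*Combined protocol and SAP*

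**What the plan says.** All of the analysis text is in the Statistical Analysis section at the end of the combined document. It first compares the groups: "Demographic, clinical, and extracted regional SUV variables were compared between the two groups using unpaired student's t-tests", "with alpha set to 0.05". The correlation step then depends on that result: "If a clinical variable differed between the two groups a Pearson's correlation was performed with it and regional SUVs".

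The only adjustment in the section belongs to another analysis. Demographic variables are screened against whole-brain SUV, and then "Significant factors were individually tested as covariates during SPM analysis". Nothing similar is stated for the correlation between clinical variables and SUV, and no other section describes that step.

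The imaging aim, in Purpose of the study (1b), is: "We hope to determine how regular cannabis use alters resting brain activity in people with MS". A difference in SUV between users and non-users is therefore what the study sets out to find.

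**The concern.** The trigger selects exactly those clinical variables that differ between users and non-users, and the study looks for SUV differences between the same groups. If both differ and the groups are pooled, part of the correlation is simply the product of two group differences. A reader shown a significant r would naturally take it to mean that people with higher or lower regional SUV have a better or worse clinical score. The pooled r alone cannot separate that from two unrelated differences between users and non-users. The reverse can also happen: a real link within groups can be diluted, or hidden if the group shifts run against it.

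**Working it through.** The plan states no effect size, SD or power for this step, so there is no figure of its own to reproduce.

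**Inputs from the documents.** Trigger: an unpaired t-test at 0.05, taken as two-sided. Group sizes: Subject Population (8a) plans 20 per group and expects that "approximately 5 from each group will not complete the study", leaving about 15. These are recruitment figures. The sessions in Study Procedures (2a) include no SUV measurement, and the Continuing review form records only 6 people studied, all users. The number with SUV data is therefore unknown.

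**Assumptions.** The group shifts, in within-group SD units, are d1 for the clinical variable and d2 for the SUV; they are written d1/d2 below. The within-group correlation is w. Data are normal and groups equal. A size of 8 per group is added to show a small imaging sample; it comes from no section of the documents.

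**Expected pooled correlation.** For equal groups:

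r = (w + d1·d2/4) / √[(1 + d1²/4)(1 + d2²/4)]

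- w = 0, 0.8/0.5: 0.10/√(1.16 × 1.0625) = 0.09
- w = 0, 0.8/0.8: 0.16/1.16 = 0.14
- w = 0, 1.0/1.0: 0.25/1.25 = 0.20
- w = 0.5, 0.8/0: 0.5/√1.16 = 0.46
- w = 0.5, 1.5/0: 0.5/√1.5625 = 0.40
- w = 0.5, 0.8/−0.8: (0.5 − 0.16)/1.16 = 0.29
- w = 0.5, 1.0/−1.0: (0.5 − 0.25)/1.25 = 0.20

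**How often the pooled r is significant when w = 0.** I simulated 2 million studies per setting, kept those where the clinical t-test gave p<0.05 (the plan's trigger), and tested the pooled r on 2n−2 df and the group-partialled r on 2n−3 df, with n per group.

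| d1/d2 | 20 per group | 15 per group | 8 per group |
|---|---|---|---|
| 0.8/0 | 5% | 5% | 5% |
| 0.8/0.3 | 7% | 7% | 6% |
| 0.5/0.5 | 9% | 9% | 8% |
| 0.8/0.5 | 10% | 9% | 8% |
| 0.8/0.8 | 17% | 15% | 13% |
| 1.0/1.0 | 27% | 23% | 18% |

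The group-adjusted test rejects in 5% throughout.

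Restricting further to regions whose SUV t-test is also p<0.05, the pooled rate over the settings 0.5/0.5 to 1.0/1.0 is about 15–29% at 20 per group, 16–27% at 15 and 22–29% at 8.

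**Masking, w = 0.5 with opposing shifts.** Share of triggered analyses that detect the link:

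| d1/d2 | 20: pooled | 15: pooled | 8: pooled |
|---|---|---|---|
| 0.8/−0.5 | 58% | 42% | 18% |
| 0.8/−0.8 | 36% | 23% | 9% |
| 1.0/−1.0 | 17% | 10% | 4% |

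The adjusted test detects it in about 91%, 80% and 44–46% respectively.

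**The case against.** The strongest reply is that the section never says the groups were pooled. If the correlations were run within groups, the statistical problem disappears and only a gap in reporting remains. That stands, and the conclusion is conditional on it.

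Second, where both variables differ by group, the overall correlation is truly non-zero, so Pearson's test of it is valid. The 17% and 27% are errors only if someone claims a within-group link, and the section makes no such claim. This also stands: the point concerns what r can be taken to show. But the section states no purpose for the step, and linking a clinical measure to regional brain activity is the obvious use of the result.

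Third, every size is assumed. At modest shifts the rates are 5–10%, and masking needs a strong within-group link running against the group shifts, which nothing in the documents suggests. The rates also apply only once the step is triggered. At 8 per group and 0.8/0.5, the trigger fires in 32% of studies, so trigger and significant r occur together in 0.32 × 0.082 = 2.6% per variable and region. These points limit the weight of the concern without removing it.

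Last, adjustment can cost power, and the part of the correlation it removes could matter if cannabis use acts on both variables through one pathway. That is a reason to keep the pooled r as well.

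**Conclusion.** The concern holds, as a minor point. The step is described without any account of group, and if one correlation was run across both groups, a significant r does not by itself show that regional SUV and the clinical variable are related within users or within non-users. With no within-group link, the pooled r is significant in 5–10% of triggered analyses at modest shifts and 13–27% when both variables shift by 0.8 to 1.0 SD, over 8 to 20 per group. If the SUV does not truly differ by group and there is no within-group link, the rate stays at 5%; if there is a link, r is attenuated.

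These figures rest on assumed shifts, normal data, equal groups and an unknown imaging sample. The step is conditional and exploratory, and the SUV t-tests, Cohen's D and the SPM analysis do not depend on it.

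**What to change.** State whether the correlation was pooled and how many participants per group had SUV data. Beside the pooled r, report a partial correlation controlling for group (or a regression with a group term), the within-group correlations, and a scatterplot marked by group. Do not present the pooled r alone as evidence that regional SUV is linked to the clinical variable.

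The Event History shows the protocol closed, so this is a supplementary re-run on existing data. It costs one degree of freedom: the critical |r| moves from 0.312 to 0.316 at 20 per group, 0.361 to 0.367 at 15 and 0.497 to 0.514 at 8.

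Power for w = 0.5 can move either way. With a true clinical shift of 0.8 SD and no SUV shift, adjusted against pooled is 91% vs 86% at 20 per group, 80% vs 74% at 15 and 44% vs 43% at 8. If the clinical difference was a chance finding, the adjusted test loses: 88% vs 92%, 75% vs 83% and 39% vs 53%. Within-group correlations are weak alone, with critical |r| of 0.444, 0.514 and 0.707, so they serve mainly to show direction and consistency.
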